Treating Cynophobia with Augmented Reality Exposure Therapy

[NCT ID not yet assigned]

11.04.2022

1. Call for Participation

A call for participation in the study will be made via social media platforms. Volunteers who would like to participate will be able to click on a link and register to the study if they agree to be contacted by the research team.

2. Administration of Specific Phobia Scale

The Turkish version of the Specific Phobia Scale will be administered to the volunteers of the study after they are explained the study and after they give their informed consent. They will be instructed to fill the questionnaire regarding their dog phobia. They will also be asked to fill a demographic form. Those who score above the cut-off point will be invited to the clinical and diagnostic interviews.

3. Clinical Interviews

During the clinical interviews, a clinical psychologist will interview volunteers regarding their phobia symptoms in accordance with DSM-5 criteria. With those volunteers who have a clinician confirmed phobia, a second interview will be conducted using Structured Clinical Interview for DSM-5 Disorders (SCID) to see if they have a mental disorder such as psychosis, substance use disorder, or epilepsy. Those participants who will be included in the study will be contacted and invited to the laboratory.

4. Explanation of the Principles and Obtaining the Informed Consent

Both groups will be invited to the laboratory for the baseline measurement. Upon their arrival, the study will be explained to them and why it is necessary to have a baseline measure of their phobia severity by seeing a real dog. The briefing and explanation will follow above-given 3 paragraphs:

We explain to the participants that their phobia is just illogical, not meaningless. It has been acquired through some form of learning. There are different ways of learning. People may learn socially, by talking to people or just observing them. People learn also through experience. We explain that for whatever reason the participant's brain has associated dogs with danger. The exposure we will be doing works in a similar way that parents hold their kid's hand and open the closet to show them there is no monster under the hood.

We have to do the same to our brain. It has to unlearn the previous learning that dogs are dangerous. In other words, the brain has to learn by experience that its feared object is actually safe by spending safe time with it. That's the basic principle of exposure therapy. We gradually expose a person to what they're afraid of until the brain gradually learns it's

safe and the fear goes away. We also explain that exposure therapies are very effective. By conducting it with AR, we offer our participants the feeling of safety by exposing them to a virtual dog. By means of this technology, our participants will feel a sense of total control in terms of what is going to happen. Even though they will know that the dogs are not real, the brain does not distinguish the experience in terms of learning.

After the briefing, both groups will be given a form of informed consent. After that the baseline measurements with the real dog will be taken. The participants will then be randomly assigned to either control or intervention conditions. Both groups will be informed about their groups, explained the rationale for the random assignment and control group. The control group will only be tested for baseline where the intervention group will receive Augmented Reality Exposure Therapy.

5. Real Dog Exposure to Measure the Baseline

We explain to the patients why we need to measure their progress with the real dog. To have a baseline measure of their phobia, we introduce the dog to the patient. When the patients stand 7 meters away from the real dog we encourage them to walk closer by saying "Is that it or do you think you can approach more?". If they can go closer to the dog, we say "Can you hold your hand close to it? Can you touch it?" When the participants reach the limits of their comfort zone that is they can not approach closer, we ask whether they would like to finish the testing.

The distance participants can approach the dog will be measured in terms of meters, the Behavioral Approach Test (BAT). Any physical contact with the dog will be measured visually for exclusion criteria i.e., the participants who can touch the dog will be excluded from the study based on the reasoning that they do not have a real phobia.

The Skin Conductance Response (SCR) will be measured to see physiological stress of the individuals via Shimmer3 GSR+ device placed on one finger. At the same time, participants will report how stressed they are (subjective unit of distress, SUD).

Participants will then be randomly assigned to either control or intervention conditions. Both groups will be informed about their groups, explained the rationale for random assignment and control group.

We say "Now you are comfortable with all these dogs, let's see how you will do with the real dog. I'm excited to see how you'll do."

6. Rooms for the Intervention

We will use two rooms for the intervention. Both rooms have enough clear space on the floor to eliminate the risk of obstruction by objects and also to have better render the AR dogs.

The first room for the intervention is bigger than the second room. The rationale for the difference is that we aim to generalize the exposure learning in the first room to broader and different contexts. Thus, we have two different looking rooms of different sizes.

7. The Intervention with the Augmented Reality Headset

a. The First Room

- Patient stands or sits in a corner of the room.
- We place one breed of dog at the furthest corner of the room (We have 3 dog breeds in various sizes we can modify).
- We ask the patients how scared they are out of 10, that is their Subjective Unit of Distress (SUD). Based on their level of fear we go on adjusting (Minimum to continue is 5/10).
- We start with one dog and then we put the other breeds next to it. We keep asking them what their SUDs are. Then we determine which one is the least scary to the patient and proceed with it only.
- We say "It is not going to get close to you, it is just going to move horizontally." Then, we move the dog horizontally a little bit. We keep repeating it until the participants' SUDs go down.
- When SUDs go down, we say "The dog is going to walk towards you a little bit or closer to you a little bit" (We keep repeating that).
- The dog comes to the middle of the room and starts moving horizontally.
- When their SUDs decrease, we add the second dog. Both dogs move horizontally.
- Then the third breed is added and makes the same horizontal movement.
- We then ask the patient to choose a breed of their liking to stay.
- We then say "Let's go walk towards it a little bit." and "Can you go with me?" and we go with the patient whilst monitoring their SUDs.
- We say "Let's stay here" and "Can you sit there?" (during this stage, we talk and joke with the patients to help them relax)
- We then include patients' cognitive processing. We ask the patient to describe the dog. We say for example "Can you tell me where the dog's head and tail are?"

- After the patient is comfortable and sitting close to the dog, we move the dog horizontally.
- We then add “Let’s see if you can touch its head or hold your hands close to it”. We calm and encourage the patient if needed until their SUDs go down.
- We move the dog to the far corner of the room. The dogs can perform actions such as sitting, barking, and jumping. We ask the patients to command “Sit!” to the dog and the dog sits. This way, the patient might feel a stronger sense of control over the events. Secondly, we ask the patients to command “Bark!” to the dog and the dog barks. Finally, we ask the patients to command “Jump!” to the dog and it jumps. In each turn, we ask the patients what the dogs are doing to engage their cognitive processing.
- Later, we ask the patients to call the dog near and sit. We control their SUDs and if it is below the threshold, we suggest the patients pet the dog while it is sitting.
- Finally, we say “I would put another dog here.” and put another breed of dog. “This dog will move a little bit here.” We ask the patients what the dogs are doing.
- We notify the patients that the dogs will move around and towards the person without prompts.
- In this room, we keep doing this until the SUDs get to the target SUD.
- Later, we say “Congratulations for doing this. Now, let’s go to the other room and try it there.”

b. The Second Room

- We explain to the patients that we will repeat the same exercises and start when they are ready.
- We start from the dog far away as in the first room. We ask the patients their SUDs. (Usually at that stage people state that they are comfortable).
- We bring the other dogs like it was done in the first room. We put all 3 different dogs here and there. If the patients are comfortable, we tell the patients that the dogs will walk around.
- When their SUD’s drop to 5, we say to the patients “Now, I will not give prompts about what the dogs will do. Is this all right for you?”
- Dogs will sit, walk, bark, and jump. Dogs first bark when they’re distant and they come closer and bark. During this stage, we will regularly monitor the SUDs.
- At the end, these dogs will be walking around, barking and jumping without prompt. After the patient is comfortable with the dogs’ sitting, barking, and jumping; we tell them “ We want you to feel comfortable by yourself and alone with these objects after

this intervention. So, if it is okay for you, I will leave the room and talk to you via a walky talky."

- We leave the room and talk with the patient via the walky talky.
- We say "I will put these 3 dogs and they are going to move all around you without my prompt."
- We include their cognitive processing and encourage them to describe the dogs by saying "Tell me what the dogs are doing? Tell me how many dogs are you counting? How many of them are moving, how many of them are standing or jumping?"
- When the participants are comfortable with their virtual phobic stimuli (SUD = 2) or their SUD's did not change for the last 10 minutes, we finish the intervention.

Ending

- When it's finished, we say "That is how exposure therapy works."
- We encourage them to try it at home. We say: "Watch videos and look at pictures of dogs. If you see a dog and you know it is safe, try to pet and play with them. If you see a dog on a leash walking with their owner, walk by them. Don't avoid it."
- Finally, we ask them to come back for the next measurement.

8. Follow-Ups

- At 1 week and 1 month follow-ups, we contact the participants and invite them to the lab. We test them using the real dog to confirm if their gains are maintained. We use the same measures and protocol as the 6th step, Real Dog.

9. Statistical Analysis

Data will be analyzed by using a statistical software called IBM SPSS 26.0. Considering the groups as fixed factor, linear mixed models will be used to evaluate the effectiveness of the Augmented Reality Exposure Therapy on the primary (Behavioral Approach Task) and secondary outcome measures (Specific Phobia Scale, Skin Conductance and Subjective Units of Distress).

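### Baseline BAT is recorded before assignment, but neither the assignment as described nor the section 9 model is said to use it; in a trial of about 20 to 60 people this costs precision

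*Combined protocol and SAP*

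**What the plan says.** Random assignment appears twice. Section 4 puts the real-dog measurement first ("After that the baseline measurements with the real dog will be taken") and then states: "The participants will then be randomly assigned to either control or intervention conditions". The end of section 5, after the description of the BAT, repeats it: "Participants will then be randomly assigned to either control or intervention conditions". Neither place gives a ratio, a method of generating the sequence, blocks, strata, minimisation or concealment.

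Section 5 defines the baseline variable: "The distance participants can approach the dog will be measured in terms of meters". The test starts far from the animal ("When the patients stand 7 meters away from the real dog we encourage them to walk closer"), and contact is an exclusion ("the participants who can touch the dog will be excluded from the study"). Among those assigned, baseline distance can therefore lie anywhere from just above 0 m to 7 m.

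Section 9 names the BAT as the primary outcome and gives the model in one sentence: "Considering the groups as fixed factor, linear mixed models will be used to evaluate the effectiveness". It mentions no baseline covariate, time term or group-by-time term. No sample size, power, alpha or BAT standard deviation is stated anywhere.

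**The concern.** When a participant is assigned, the plan already holds that person's baseline value of the primary outcome, which is likely to be among the best predictors of the follow-up value. As written, it is used neither to balance the arms nor to adjust the comparison.

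If assignment amounts to a coin toss and the sample is modest, the arms can begin at visibly different distances from the dog. In a comparison on group alone, part of that starting gap passes into the follow-up difference. What is at stake is precision, and the credibility of a result whose baseline table shows unequal arms. Unequal arm sizes are a smaller part of the same point.

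**Working it through.** The plan states no figure to reproduce. Inputs from the documents are the order of events (baseline, then assignment), the 0 to 7 m range, and group as the only named fixed factor. Assumptions are simple 1:1 assignment, total N from 20 to 100, an SD of 2 m where metres are shown (a uniform spread over 0 to 7 m has SD 7/√12 = 2.0 m), and a correlation r of 0.5 to 0.7 between baseline and follow-up BAT.

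**1. Chance of a baseline gap.** With equal arms, the standard error of the baseline mean difference is SD × √(4/N), and P(gap > 0.5 SD) = 2 × [1 − Φ(0.5/√(4/N))]. For N=30, √(4/30) = 0.365, 0.5/0.365 = 1.37, and P = 17%. The simulated columns use a normal baseline. The simple column also lets arm sizes vary; the stratified column uses two strata cut at the median and blocks of 4.

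| Total N | Formula | Simulated, simple | Simulated, stratified | 95% limit of gap, SD 2 m |
|---|---|---|---|---|
| 20 | 26% | 27% | 8% | 1.75 m |
| 30 | 17% | 18% | 3% | 1.43 m |
| 40 | 11% | 12% | 1% | 1.24 m |
| 60 | 5% | 6% | under 1% | 1.01 m |
| 100 | 1.2% | – | – | 0.78 m |

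The last column is 1.96 × 2 × √(4/N). For SDs of 1 to 2.5 m it runs from 0.88 to 2.19 m at N=20 and from 0.39 to 0.98 m at N=100.

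**2. What a gap does to a group-only comparison.** A gap of 0.5 SD shifts the follow-up difference by r × 0.5 SD, which is 0.7 × 0.5 = 0.35 SD at r=0.7.

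**3. Gain from adjusting for baseline.** With simple assignment and a normal covariate, the variance of the adjusted contrast relative to the group-only contrast is (1 − r²) × [1 + 1/(N − 4)]. At N=30 the bracket is 27/26 = 1.038.
- r=0.5: 0.75 × 1.038 = 0.78, a cut of 22%.
- r=0.7: 0.51 × 1.038 = 0.53, a cut of 47%.
- Break-even is r² = 1/27, or r = 0.19; below that, adjustment costs at most about 4%.

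**4. Gain from stratifying.** At N=30 the SD of the baseline difference falls from 0.370 to 0.231 SD, a variance reduction of 1 − (0.231/0.370)² = 61%. With a group-only model this cuts the variance of the contrast by about 17% (r=0.5) to 29% (r=0.7), less than adjustment alone. Once baseline is in the model, stratifying only shrinks the 1/26 term: 1 − (1 + 0.39/26)/(1 + 1/26) = 2%. Counting the more equal arm sizes as well brings this to about 5%.

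**5. Arm sizes.** From Binomial(N, 0.5), a split of one third to two thirds or worse has probability 11.5%, 9.9% and 3.8% at N=20, 30 and 40. The cost is small: a 60:40 split keeps 4 × 0.6 × 0.4 = 96% of the efficiency of equal arms.

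**6. Where the strata are cut.** With a cut that divides participants 90:10, the stratified figure is about 21% at N=20 (27% simple) and about 11% at N=30 (18% simple). A poorly placed cut loses much of the benefit.

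**The case against.** A reader might infer that the plan has chosen plain, unrestricted randomisation in a small trial. The documents support neither half. They leave the method unstated, so blocks or strata may be intended, and they give no sample size. At N=100 a gap above 0.5 SD has a chance of about 1%, and at N=200 under 0.1%.

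A reader might also infer that a chance gap biases the result. Under valid randomisation it does not do so on average, and the error rate of the test already allows for it.

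It can also be said that a mixed model for a measure taken at baseline, 1 week and 1 month would naturally include time, and so deal with a starting gap. That is a fair reading, but section 9 does not state it, and it is not equivalent to adjustment. With equal variances, an unconstrained group-by-time contrast from baseline is a comparison of change scores, whose variance relative to the group-only contrast is 2(1 − r). That is 1.00 at r=0.5, no gain, and 0.60 at r=0.7, a 40% cut. Adjustment gives 22% and 47%.

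Finally, adjustment alone secures nearly all the benefit, so stratification is optional. That stands, and it sets the order of the fixes below.

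**Conclusion.** The point holds as a gap in what is specified, of moderate importance. Nothing stated in sections 4, 5 or 9 makes use of the baseline BAT. If assignment is simple and total N is about 20 to 60, a baseline gap above 0.5 SD has roughly a 27% to 6% chance, and a group-only comparison gives up precision that baseline adjustment would recover: about 22% to 47% of the variance at N=30. The issue of chance imbalance is minor by N=100. These figures rest on assumed N, r and baseline distribution, and on assignment being simple.

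The point is also conditional. Section 4 says that controls are tested only at baseline. Read literally, there is then no control follow-up BAT to compare or adjust. That statement must be reconciled with the between-group analysis in section 9 before this point has any effect.

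**What to change.** **First, in section 9 (free).** State that follow-up BAT is modelled with baseline BAT distance as a covariate alongside group, and name the time terms. The cost is one sentence and one degree of freedom.

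**Second, in sections 4 and 5 (cheap, optional).** State the sample size and the assignment method. If stratification is wanted, replace both assignment sentences with wording such as: after the baseline BAT distance is recorded, participants are assigned 1:1 from a concealed, computer-generated list in randomly varying blocks, stratified by baseline distance in two bands. Set the cut near the median expected in this population rather than fixing it at 3.5 m, half of the start distance. Keep the stratum or the baseline distance in the model so that the standard error reflects the design. This needs a two-list allocation file and must be settled before the first assignment. The downside is that the next allocation becomes slightly easier to guess, since participants are told their group; varying block sizes and concealment limit this.

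**Before either,** reconcile the section 4 statement on testing of the control group with the planned group comparison.

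### As written, controls are tested only at baseline, so the mixed model with group as fixed factor cannot identify the treatment effect

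*Combined protocol and SAP*

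**What the plan says.** Section 4 puts consent first, then the real-dog baseline, then random assignment, and goes on: "The control group will only be tested for baseline where the intervention group will receive Augmented Reality Exposure Therapy".

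The later measurements are described in three places:

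- The Ending part of Section 7, which closes the augmented reality session: "Finally, we ask them to come back for the next measurement".
- Section 8: "At 1 week and 1 month follow-ups, we contact the participants and invite them to the lab", with the purpose "We test them using the real dog to confirm if their gains are maintained". No arm is named.
- The end of Section 5, in a line spoken to people who have become comfortable with the virtual dogs: "see how you will do with the real dog". This implies an immediate post-session test that is scheduled nowhere else.

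Section 9 then says: "Considering the groups as fixed factor, linear mixed models will be used to evaluate the effectiveness of the Augmented Reality Exposure Therapy". The primary outcome is the behavioural approach distance (BAT). The secondary outcomes are the Specific Phobia Scale, skin conductance and subjective distress. Section 9 names no time factor, group-by-time term, visit or contrast.

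The Specific Phobia Scale appears in the schedule only at screening (Section 2): "The Turkish version of the Specific Phobia Scale will be administered to the volunteers of the study". Section 8 repeats the real-dog measures, which Section 5 lists as BAT, skin conductance and distress.

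**The concern.** A randomised comparison needs outcome data from both arms after randomisation. On the literal wording, the only control measurement is taken before it. The request to return comes at the end of a session that controls never attend, and the stated purpose of follow-up, checking that gains last, fits treated people only.

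The treated arm's change would then have no comparator. Such change can arise without treatment. The real-dog approach test is itself repeated. Participants are also selected on it, because Section 5 excludes anyone who can touch the dog at baseline, so some regression to the mean is possible. All of this would be credited to the therapy. Control data not collected at 1 week and 1 month cannot be recovered afterwards.

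**Working it through.** The plan gives no sample size, SD or effect size, so there is no figure of its own to reproduce. The question is one of identifiability, which needs none of these.

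**Inputs.** Control schedule: baseline only (Section 4) or also the Section 8 visits (the other reading). Treated schedule: baseline, 1 week and 1 month (3 visits), or 4 visits if the immediate test implied in Section 5 takes place.

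**Notation.** τ is the treatment effect and δ the change that would occur without treatment, both in metres of closer approach. Each is taken as the same at every post-baseline visit. Visits are complete and participants have a random intercept. Baseline means are equal in expectation, because baseline precedes randomisation.

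**Group-by-visit model.** With V visits there are 2V parameters. The rank equals the number of arm-by-visit cells observed.

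- Controls at baseline only, V = 3: cells 1 + 3 = 4, parameters 6.
- Controls at baseline only, V = 4: cells 1 + 4 = 5, parameters 8.

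Forcing a common baseline mean does not help: the ranks become 3 of 5 and 4 of 7. Only τ + δ is identified, in the treated arm.

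**Group-only model.** The expected coefficient is the treated mean over visits minus the control mean over visits. Controls at baseline only:

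- V = 3: (2/3)(τ + δ) − 0 = 0.667(τ + δ)
- V = 4: (3/4)(τ + δ) − 0 = 0.75(τ + δ)

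Controls also at the Section 8 visits:

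- Both arms at 3 visits: (2/3)(τ + δ) − (2/3)δ = 0.667τ
- Treated at 4 visits, controls missing the immediate test: (3/4)(τ + δ) − (2/3)δ = 0.75τ + 0.083δ

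| Controls | Treated | Rank / parameters, group-by-visit | Contrasts estimable | Group-only coefficient |
|---|---|---|---|---|
| Baseline | 3 visits | 4 / 6 | 0 of 2 | 0.667(τ + δ) |
| Baseline | 4 visits | 5 / 8 | 0 of 3 | 0.75(τ + δ) |
| 3 visits | 3 visits | 6 / 6 | 2 of 2 | 0.667τ |
| 3 visits | 4 visits | 7 / 8 | 2 of 3 (not the immediate test) | 0.75τ + 0.083δ |

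**Group + visit model, controls at baseline only.** Visit effects are estimated from the treated arm alone and absorb τ + δ. The group coefficient is then the baseline difference, with expectation 0 whatever τ is.

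**Sensitivity.** The coefficients do not change at correlations of 0.2, 0.5 or 0.8, or with 10:30 or 30:10 allocation. Under AR(1) errors with correlation 0.3 to 0.9, the weight in the first two rows is 0.52 to 0.63 (3 visits) or 0.55 to 0.71 (4 visits). It is still identical for τ and δ.

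**Illustration, with assumed δ.** Take τ = 0 and δ = 0.5 to 2 m, on a test that starts at 7 m. With 3 visits the group-only coefficient is 0.667 × 0.5 = 0.33 m to 0.667 × 2 = 1.33 m. With 4 visits it is 0.75 × 0.5 = 0.38 m to 0.75 × 2 = 1.50 m.

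The 3-visit case was also simulated with τ = 0, 15 to 30 per arm, total SD 1, intraclass correlation 0.5 and 300 runs per setting (all assumed). The group term was rejected at nominal 5% in 15% to 32% of runs for δ = 0.5 SD, and in 52% to 78% for δ = 1 SD.

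**The case against.** The Section 4 sentence may describe only that laboratory visit, with the word only meaning tested but not treated. Sections 4 and 5 use the word participants for both arms, Section 5 says "We explain to the patients why we need to measure their progress with the real dog", and a randomised comparison with a group factor makes sense only if controls return. On that reading Section 8 covers everyone and nothing conflicts. This is possible, but it strains against the word only, the purpose given in Section 8 and the place of the return invitation. If it is what was meant, the text should say so, because staff following the protocol could reasonably not recall controls. Section 8 also refers to the sixth step for the real-dog test, which is in Section 5, so the numbering does not settle the matter.

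It is also fair that Section 9 does not say group is the only fixed effect. The group-only figures therefore describe one possible model. The rank result does not depend on that choice: under the literal schedule, adding time terms does not restore the contrast.

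Two limits stand. If controls return, a group-only term understates the effect (67% of it) only when both arms have the same visits. With an extra treated-only test the coefficient also carries 0.083δ, and exceeds τ if δ is more than three times τ. The four-visit results rest on an immediate test inferred from a single, possibly misplaced line.

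**Conclusion.** The concern holds and must be fixed before controls' follow-up dates pass. As written, no post-baseline group contrast is estimable on the BAT, nor on the other real-dog measures, which follow the same schedule. A group coefficient can still be computed, but it equals (a fraction of) the treatment effect only if untreated participants do not change. The plan does not state that assumption, and baseline-only controls cannot test it. The Specific Phobia Scale has no post-baseline measurement scheduled in either arm.

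If Section 8 was meant to include controls, the 1-week and 1-month effects are estimable. Sections 4 and 8 must then be reconciled, and Section 9 must still name the time terms and the contrast.

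The rank results need no numerical assumption. The coefficient weights assume complete visits, a random intercept, and the same τ and δ at each post-baseline visit. The metre and rejection figures are illustrations on assumed inputs.

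**What to change.** 1. **Section 4.** Replace the sentence on controls with: *The control group receives no augmented reality exposure but completes the same real-dog test (BAT, skin conductance, subjective distress) at the same post-baseline time points as the intervention group.*
2. **Section 8.** State that both groups attend the 1-week and 1-month visits. State whether there is an immediate post-session real-dog test and, if so, when controls take it. State when the Specific Phobia Scale is repeated in both groups. Correct the cross-reference to the real-dog test.
3. **Section 9.** State: *Each mixed model includes group, time (categorical) and group-by-time as fixed effects and a participant random intercept. The primary contrast is the group difference in change in BAT distance from baseline to [one stated visit].*
4. **Fallback.** If controls cannot be retested, restate Section 9 as an uncontrolled pre-post analysis and drop the between-group effectiveness claim.

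With both arms at every visit, the group-by-visit model has full rank: 6 of 6 with three visits, 8 of 8 with four.

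The cost is rewording, a matching change to what controls are told at consent, control return visits using the existing test, and one questionnaire per chosen visit in both arms. Untreated phobic volunteers would meet the real dog again and some may drop out, so drop-out should be reported by arm. Section 5 already asks participants at their limit whether they wish to finish the test.

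### The primary approach-distance test sets no limit on tester prompts and carries a cue that only treated participants can receive, which can inflate the apparent effect

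*Combined protocol and SAP*

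**What the plan says.** Section 9 makes approach behaviour the primary outcome: the model is to assess the "effectiveness of the Augmented Reality Exposure Therapy on the primary (Behavioral Approach Task) and secondary outcome measures". Section 5 defines the measurement: "The distance participants can approach the dog will be measured in terms of meters, the Behavioral Approach Test (BAT"), starting 7 m from the dog.

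The distance is obtained under prompting. Staff are told "we encourage them to walk closer by saying 'Is that it or do you think you can approach more", and those who do come closer are asked "Can you hold your hand close to it? Can you touch it". The test winds down when participants reach the edge of their comfort, "that is they can not approach closer, we ask whether they would like to finish the testing". The plan gives no number of prompts, no interval between them and no maximum duration.

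Allocation is open: "Both groups will be informed about their groups, explained the rationale for random assignment and control group". The whole document is written as 'we', covering the briefing, the augmented reality (AR) session and the real-dog test. It names no separate or masked tester.

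Section 5 closes with a line to be spoken to the participant. It takes for granted that the participant is now at ease with the dogs already shown, invites them to "see how you will do with the real dog", and adds that the speaker is excited about the result.

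Section 8 carries the procedure to 1 week and 1 month: "We use the same measures and protocol as the 6th step, Real Dog". Step 6 is in fact the description of the rooms; the real-dog test is Section 5. Section 4 says the control arm is tested at baseline only, while Section 8 invites participants back without naming an arm.

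**The concern.** Approach distance under encouragement depends partly on the participant's fear and partly on how long the tester persists. If persistence or expectation differs by arm, the difference enters the outcome in metres, the same units as the treatment effect.

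Baseline testing comes before randomisation, so arm-dependent prompting can arise only in later tests, and adjusting for baseline cannot remove it. Nor can the mixed model in Section 9: a shift that follows arm is absorbed by the group term. Participants cannot be masked to AR treatment, which leaves the tester's behaviour as the part of the measurement that the plan can control.

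The closing line of Section 5 is the most specific difficulty. The rest of the script could be delivered identically to everyone. That line could not, because a control has met no virtual dogs.

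**Working it through.** **The text, set side by side**

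1. Prompt wording: scripted (Section 5). Number, spacing and duration: not stated.
2. End of test: the participant's own limit, after which staff ask whether to stop. There is no objective criterion.
3. Tester: not specified. The plan neither says that the therapist tests nor excludes it.
4. Cue specific to one arm: present, at the end of Section 5, just after the statement on randomisation.
5. Control follow-up: Section 4 says baseline only; Section 8 does not name an arm.

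Items 1 to 3 leave room for differential prompting without directing it. Item 4 is a difference between arms in the text itself. Item 5 decides where a bias would appear. If controls are retested, it is in the between-arm difference. If they are not, it is in the treated arm's change from baseline, with no concurrent control to set against it.

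**Illustration of size**

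The plan states no sample size, SD, significance level or effect, so there is no figure of its own to reproduce. Everything below is assumed: n per arm, SD, a two-sided 5% level, no true effect, and a shift b in the treated arm only. It also assumes that controls are retested. A two-sample t test stands in for the mixed model.

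- SE = SD × √(2/n)
- Noncentrality = b / SE, with 2n − 2 degrees of freedom
- False-positive rate = probability that |t| exceeds its 5% critical value under that noncentrality

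With n = 20 per arm:

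| SD (m) | SE (m) | b = 0.25 m | b = 0.5 m | b = 1.0 m |
|---|---|---|---|---|
| 2.0 | 2.0 × √0.1 = 0.63 | 6.7% | 12.0% | 33.8% |
| 1.5 | 1.5 × √0.1 = 0.47 | 8.1% | 17.7% | 53.8% |

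For example, with SD 2.0 m and b = 0.5 m the noncentrality is 0.5/0.632 = 0.79, which gives 12.0%. The normal approximation gives 12.4% there, and 18.4% for SD 1.5 m, so the choice of test matters little.

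Over 10 to 30 per arm and SD 1.0 to 2.5 m, a 0.5 m shift gives about 7% to 48%. On the 7 m scale, 0.5 m is 0.5/7 = 7%. With no shift the rate is 5%.

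**The case against.** A reader might infer that the plan prescribes unlimited prompting by an unmasked therapist. It does not. The prompts are worded questions, there is an end cue, and nobody is told to repeat the prompts indefinitely. The 'we' is the voice of the whole document and does not show that one person both treats and tests. Read literally, the prompts and end cue are the same for everyone, and bias from them would need staff to use their discretion differently by arm. All of this stands. The supportable statement is that the plan permits these things, not that it orders them.

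The line about being at ease with the dogs may be misplaced text, since it sits in a baseline section before any AR session has been described. That is plausible. But its wording points to a real-dog test after treatment, and Section 8 reuses the real-dog procedure, so as written it can reach the outcome test.

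A reader might also infer a certain between-arm bias. That assumes controls are retested, which Section 4 appears to exclude. The objection is right that the two-arm calculation applies only if they are. If they are not, the distortion moves to the within-arm gain.

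Finally, the shift, SD and sample size are all assumed, and nothing in the documents suggests that coaching adds any particular distance. That also stands: the figures show sensitivity and do not predict the bias.

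What the objection does not remove is that the primary measure has an unlimited tester input and an arm-specific cue, both of which can be closed by wording.

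**Conclusion.** The point holds in this limited form. The primary distance is obtained under encouragement with no limit on prompts or time, in an open trial with no rule separating tester from therapist, and Section 5 contains an expectation cue that fits the treated arm only. This can inflate the apparent effect, in the between-arm difference or in the within-arm gain, depending on how the conflict over control testing is resolved.

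The documents do not show that such a bias will occur, or how large it would be. The rise from 5% to about 12% to 18% rests on an assumed 0.5 m shift, 20 per arm, SD of 1.5 to 2.0 m, no true effect and retested controls. The change should be made because it protects the primary outcome at almost no cost.

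**What to change.** 1. Delete the closing line of Section 5 (the one that presumes ease with the dogs and voices excitement) from the outcome test.
2. In Section 5, state a fixed prompt sequence with a set number of prompts and a set wait. Keep the hand and touch questions conditional on approach, as now. Allow no other encouragement. Read the distance from floor marks at the final stop. Apply this identically in both arms and at every visit.
3. In Section 8, correct the reference to step 6 so that it points to the real-dog test in Section 5. Reconcile Section 4's baseline-only testing of controls with Section 8, so that it is clear both arms are retested under this same script.
4. Where existing staffing allows, have each follow-up test run by a team member who did not deliver that participant's AR session. The documents do not give the team size, so this cannot be made a firm requirement from here.

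Items 1 and 2 cost wording and floor tape. Item 4 costs a rota. If the current intention is not to retest controls, item 3 also adds their follow-up visits. The downside is that capped prompting may give slightly shorter approaches in both arms.
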